5.3.3.5 Immune-related Myocarditis

Monitor subjects for myocarditis prior to and periodically during treatment. For all grades of myocarditis, permanent treatment discontinuation should be discussed. Cardiology should be consulted, and high dose corticosteroids should be administered (1 to 2 mg/kg of prednisone initiated rapidly (oral or IV depending on symptoms). In subjects without an immediate response to high-dose corticosteroids, consider cardiac transplant rejection doses of corticosteroids (methylprednisolone 1 g every day) and the addition of either mycophenolate, infliximab, or anti-thymocyte globulin. Permanently discontinue for any >Grade 2 myocarditis.

5.3.3.6 Immune-related Adrenal Insufficiency

Monitor for signs and symptoms of adrenal insufficiency. Evaluate adrenocorticotrophic hormone (ACTH) (a.m.), cortisol level (a.m.), and metabolic panel (sodium, potassium, carbon dioxide, and glucose). Consider ACTH stimulation test for indeterminate results. For evidence of primary adrenal insufficiency (high ACTH, low cortisol), evaluate for a precipitating cause of crisis, such as infection, and perform an adrenal CT scan for metastasis/hemorrhage. For Grade 1 adrenal insufficiency, treatment may be held until subject is stabilized on replacement hormone.

Withhold study treatment for Grade 2, Grade 3, or Grade 4 events until the subject is stabilized on replacement hormones. Endocrinology should be consulted for all grades of adrenal insufficiency including for recommendations on replacement and stress dose steroid therapy.

5.3.3.7 Immune-related Type 1 Diabetes

Monitor subjects for hyperglycemia or other signs and symptoms of new or worsening diabetes mellitus, including measuring glucose at baseline. Laboratory evaluation in suspected Type 1 diabetes should include testing for ketosis in urine and an assessment of the anion gap on a metabolic panel. Withhold study treatment for Grade 2, Grade 3, or Grade 4 events, perform urgent endocrine consultation for all subjects, and initiate insulin therapy for all subjects. Hold treatment until glucose control is obtained on therapy with reduction of toxicity to ≤Grade 1.

5.3.3.8 Immune-related Hypophysitis

Monitor for signs and symptoms of hypophysitis. Evaluate ACTH (a.m.), cortisol (a.m.), TSH, FT4, and electrolytes at baseline and determine whether hypophysitis or adrenal insufficiency is to be ruled out. Evaluate additional hormones (eg, FSH, LH, testosterone, estrogen) as clinically indicated. Consider brain imaging (pituitary/sellar cuts) if clinically indicated. Consider holding study treatment for Grade 1 events until subject is stabilized on replacement therapy. Withhold study treatment for Grade 2, Grade 3, or Grade 4 events until the subject is stabilized on replacement hormones. Endocrinology should be consulted. Be aware of the need to start corticosteroids first when planning hormone replacement therapy for multiple deficiencies.

5.3.3.9 Immune-related Uveitis and Other Ocular Inflammatory Toxicities

Counsel subject to inform the Investigator of any vision changes, eyelid swelling, proptosis, or pain. Refer to ophthalmology for all subjects (within 1 week for all subjects for Grade 1 events; urgent referral for Grade >1 events). Withhold study treatment for Grade 2 events until after ophthalmology consult. Treatment for Grade 1 uveitis includes artificial tears. Treatment for >Grade 1 events includes topical and systemic corticosteroids. Resume study treatment after return to ≤Grade 1. Permanently discontinue for Grade 3 and Grade 4 uveitis or episcleritis. Blepharitis does not have a formal grading system. Treatment includes warm compresses and lubrication drops. Study treatment may continue unless the event is persistent and/or serious.

5.3.3.10 Immune-related Encephalitis or Meningoencephalitis

Monitor for changes in neurologic function. Withhold study treatment for new onset or moderate to severe neurologic symptoms and evaluate to rule out infectious or other causes of neurologic deterioration. Withhold study treatment for Grade 1, Grade 2, or Grade 3 events and consult with neurology. Consider concurrent IV acyclovir until polymerase chain reaction (PCR) results are obtained and negative, and treatment with methylprednisolone and additional treatment (eg, IV immunoglobulin, rituximab as recommended by neurology consultation). Permanently discontinue treatment for confirmed diagnosis of autoimmune encephalopathy.

5.3.3.11 Immune-related Skin Toxicity

For rash and inflammatory dermatitis, Grade 1 toxicities should be treated with emollients and/or mild-moderate potency topical corticosteroids. Counsel subjects to avoid skin irritants and sun exposure. For Grade 2 toxicities, consider initiating prednisone (or equivalent) at 1 mg/kg, tapering over at least 4 weeks. In addition, treat with topical emollients, oral antihistamines, and topical medium to high potency corticosteroids. For Grade 3 toxicities, initiate 1 to 2 mg/kg (methyl)prednisolone (or equivalent), tapering over at least 4 weeks and treat also with topical emollients, oral antihistamines, and topical medium-high potency corticosteroids. Consult with dermatologist. For Grade 4 toxicities, treat with systemic corticosteroids IV

(methyl)prednisolone (or equivalent) 1 to 2 mg/kg with slow tapering when the toxicity resolves. Admit subject immediately with urgent consult by dermatology.

For bullous dermatoses and severe cutaneous adverse reactions refer to Brahmer et al for additional guidance ([Brahmer 2018](#)). Refer to dermatology for blisters that are not explained by infectious/transient other causes (eg, herpes simplex, herpes zoster infections, pressure/friction bullae). When symptomatic bullae or erosions are observed on the skin or mucosal surfaces, the cutaneous irAE is, by definition, considered at least Grade 2.

5.3.3.12 Other Immune-related Adverse Reactions

For any suspected immune-related adverse reactions, exclude other causes. Based on the severity of the adverse reaction, withhold study treatment, administer high-dose corticosteroids, and/or if appropriate, initiate hormone replacement therapy. Upon improvement to Grade ≤ 1 , initiate corticosteroid taper and continue to taper over at least 1 month. Consider restarting study treatment after completion of corticosteroid taper based on the severity of the event.

Refinement of the recommended treatment of TRAEs will be made as the study progresses.

If any of the immune-related symptoms worsen or do not improve with the guidelines above, tumor necrosis factor alpha (TNF α) inhibitors may be administered at the discretion of the Investigator.

5.3.4 Monitoring and Management of Infusion-related Reactions (IRRs)

5.3.4.1 Monitoring of IRRs

Subjects will be monitored for IRRs, including monitoring of vital signs as outlined in Footnote 13 of [Table 1](#) (Part A) and Footnote 16 of [Table 2](#) (Part B), during and after each study treatment infusion.

For the first 2 infusions of study treatment, subjects will be monitored for 4 hours after the completion of each infusion.

If no IRRs are noted during or after the first 2 infusions, monitoring for irAEs and vital signs will continue for 1 hour after the completion of each subsequent infusion.

After the first 2 infusions, monitoring beyond 1 hour after the infusion will be at the Investigator's discretion and in accordance with the investigational site's standard protocol.

5.3.4.2 Management of IRRs

Subjects should not receive any premedication prior to study treatment infusion, unless the Sponsor determines that the occurrence of IRRs warrants routine prophylactic treatment (which may include paracetamol/acetaminophen, histamine antagonists, and/or corticosteroids). Any subject who experiences an IRR should receive premedication (antipyretics and/or antihistamines) prior to receiving subsequent study treatment infusions. Additional premedication should be used only after review with the Medical Monitor.

Discontinue study treatment for a Grade 4 IRR or an IRR that is directly related to a Grade 4 AE.

If a \geq Grade 2 IRR is observed during or after an infusion, a local blood draw is required to measure tryptase, total immunoglobulin E, and complements C3a and C5, preferably within 2 hours and not more than 6 hours after the first signs/symptoms of the IRR.

For all allergic (hypersensitivity) reactions, including IRRs, that occur during or after study treatment administration, follow the guidelines in [Table 6](#).

If anaphylaxis occurs (see diagnostic criteria in [Appendix D](#)), appropriate medical therapy in accordance with institutional standard of care must be administered immediately, and study treatment must be permanently discontinued.

Table 6 Management of Allergic Reactions

Grade of Allergic Reaction	Treatment
Grade 1: Transient flushing or rash, drug fever <38°C (<100.4°F)	Remain at bedside and monitor subject until recovery from symptoms.
Grade 2: Intervention or infusion interruption indicated; responds promptly to symptomatic treatment (eg, antihistamines, NSAIDS, narcotics); prophylactic medications indicated for ≤24 hours	Stop the study treatment infusion. Begin an IV infusion of normal saline, and treat the subject as follows: 
 Administer diphenhydramine 50 mg IV (or equivalent) and/or paracetamol/acetaminophen 325 mg to 1000 mg PO; remain at bedside and monitor subject until resolution of symptoms. Corticosteroid therapy may also be administered as appropriate. Once symptoms have resolved, continuation of treatment is allowed with a 50% reduction of the original infusion rate; if no further complications ensue after 30 minutes, the rate may be increased to 100% of the original infusion rate. Monitor subject closely. If symptoms recur, then the infusion should be discontinued and no further study treatment will be administered at that visit. Administer diphenhydramine 50 mg IV and remain at bedside and monitor the subject until resolution of symptoms. Premedication (diphenhydramine and paracetamol/acetaminophen) may be given prior to subsequent treatment cycles after review with the Medical Monitor.
Grade 3: Prolonged (eg, >6 hours, not rapidly responsive to symptomatic medication and/or brief interruption of infusion); recurrence of symptoms following initial improvement; hospitalization indicated for clinical sequelae (eg, renal impairment, pulmonary infiltrates)	Immediately discontinue infusion of study treatment. Begin an IV infusion of normal saline, and treat the subject as follows: 
 Recommend bronchodilators, epinephrine 0.2 to 1 mg of a 1:1000 solution for subcutaneous administration or 0.1 to 0.25 mg of a 1:10000 solution injected slowly for IV administration, and/or diphenhydramine 50 mg IV with methylprednisolone 100 mg IV (or equivalent), as needed. Subject should be monitored until the Investigator is comfortable that the symptoms will not recur. Study treatment will be permanently discontinued unless continuation of therapy is believed to provide potential clinical benefit and no other reasonable alternatives exist, then re-challenge may be pursued at the discretion of the Investigator after consultation with the Medical Monitor.
Grade 4: Life-threatening consequences; urgent intervention indicated	Follow treatment for Grade 3 allergic reaction and monitor subject until recovery from symptoms. Study treatment will be permanently discontinued .

IV = intravenous; NSAID = nonsteroidal anti-inflammatory drug; PD-L1 = programmed death ligand 1; PO = *per os*, by mouth.

During an IRR, vital signs will be obtained every 2 to 5 minutes until stable. In the case of late-occurring hypersensitivity symptoms (eg, appearance of a localized or generalized pruritus within 1 week after treatment), symptomatic treatment may be given (eg, oral antihistamine or corticosteroids).

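### In Table 6, an infusion reaction that resolves and recurs on restart falls under both the Grade 2 and the Grade 3 row, whose defaults for later treatment differ, and no text says which row applies

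*Combined protocol and SAP*

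**What the plan says.** Section 5.3.4.2 of the protocol gives Table 6 a wide scope: "For all allergic (hypersensitivity) reactions, including IRRs, that occur during or after study treatment administration, follow the guidelines in" Table 6.

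For a Grade 2 reaction, the table has the infusion stopped and the symptoms treated. Then: "Once symptoms have resolved, continuation of treatment is allowed with a 50% reduction of the original infusion rate". If the reaction returns: "If symptoms recur, then the infusion should be discontinued and no further study treatment will be administered at that visit". The row ends with "Premedication (diphenhydramine and paracetamol/acetaminophen) may be given prior to subsequent treatment cycles after review with the Medical Monitor".

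The Grade 3 row defines its grade by several alternatives, one of which is "recurrence of symptoms following initial improvement". Its consequence is: "Study treatment will be permanently discontinued unless continuation of therapy is believed to provide potential clinical benefit and no other reasonable alternatives exist". If those conditions are met, "re-challenge may be pursued at the discretion of the Investigator after consultation with the Medical Monitor".

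The Grade 4 row stops treatment permanently and states no exception.

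**The concern.** The Grade 2 row itself allows the infusion to be restarted and then says what to do if symptoms return. That sequence, improvement followed by return of symptoms, also fits one of the Grade 3 criteria. A site that stays in the Grade 2 row ends the infusion for the day and has no instruction to stop later cycles. A site that moves to the Grade 3 row stops study treatment for good unless its conditions for re-challenge are met.

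This text is used at the bedside during a reaction, at about 40 sites (Section 3.2). Study treatment means both drugs (Section 5.1), and Section 5.3.2 adds that stopping CX-072 also stops ipilimumab. Section 7 lists discontinuation for toxicity among the safety variables, so differing site practice could enter a reported result as well as the care of the individual subject.

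**Working it through.** There is no plan figure to reproduce. The check is a comparison of the two rows for one defined event: a reaction first handled as Grade 2 that resolves on treatment and recurs after the infusion is restarted.

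**Step 1: does the event meet both rows?** It meets the Grade 2 row because that row names recurrence after restart. It meets the Grade 3 definition because symptoms that resolved and came back have recurred after improvement. The Grade 3 criterion stands as a separate alternative and is not limited to recurrence without a restart.

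**Step 2: do the rows lead to the same place?**

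| | Grade 2 row | Grade 3 row |
|---|---|---|
| Acute management on recurrence | Infusion ended; IV diphenhydramine and bedside monitoring until symptoms resolve | Infusion ended; saline, with an as-needed list that includes bronchodilators, epinephrine, and diphenhydramine with methylprednisolone |
| Default for later dosing | Restriction stated for that visit only; premedication "may be given prior to subsequent treatment cycles after review with the Medical Monitor" | Permanent discontinuation |
| Condition for further dosing | No benefit test; Medical Monitor review is attached to premedication | Belief in potential benefit, no other reasonable alternative, Investigator discretion and Medical Monitor consultation |

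The rows differ on all three lines.

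**Step 3: does other text decide between them?**
- The running text of Section 5.3.4.2 names Grade 4 reactions, reactions directly related to a Grade 4 AE, and anaphylaxis as reasons to discontinue. It does not address recurrence on restart.
- Table 5 has no row for infusion reactions. Its general row for other Grade 3 adverse reactions says to hold treatment until recovery, which presupposes that the grade is already known.
- No readable text says that the higher grade governs. If it did so for the whole event, the Grade 2 sentence on recurrence would have no case left to cover.

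**Step 4: what is one subject worth?** Sections 3.2 and 3.3 give 14 subjects in Stage 1 of Cohorts A1, A3 and B1, 40 in Stage 1 of Cohort A2, and about 40 in total (38 to 48) for the other cohorts.
- 1/14 = 7.1 percentage points
- 1/40 = 2.5 percentage points (1/38 = 2.6; 1/48 = 2.1)

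These are the shifts in a cohort's discontinuation rate if one subject is stopped under one row and continued under the other. The documents give neither the rate of Grade 2 infusion reactions nor the share that recur on restart, so no expected count is offered.

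**The case against.** The strongest reply is that the rows can be read as compatible: Grade 2 gives the immediate action when symptoms return, and Grade 3 then governs later treatment. In support, the Grade 2 row never expressly says that a subject with a recurrence goes on to later cycles. Its premedication sentence also serves subjects whose reaction did not recur. This stands in part: the route to later cycles is an inference. But it is the natural one, because the restriction is tied to a single visit. The compatible reading also does not explain why the two rows prescribe different acute management for the same event.

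A second reply is that both rows mention the Medical Monitor, so the matter would be settled by a call. In the Grade 2 row, however, that review attaches to premedication and not to the decision to dose again.

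A third reply concerns grading. A reader might infer that the choice of row decides the recorded AE grade, and with it the rate of AEs of Grade 3 or higher. The documents do not support this. Section 9.2.2 says AEs are graded by CTCAE v5.0, with Table 7 as the fallback; Table 6 is a management table. This reply stands, and no effect on the Grade 3 or higher rate is claimed.

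**Conclusion.** The overlap is real, and following the table as written gives two conflicting defaults for one event. A reader might go further and take the Grade 3 row as an absolute stop set against a Grade 2 permission to continue. The text does not support that: Grade 3 carries a written re-challenge exception, and only Grade 4 stops without one. The conflict lies in acute management, in the default for later dosing and in the conditions for continuing.

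The consequence is possible variation between sites in how the same reaction is handled, with a bearing on subject safety and on discontinuation for toxicity. Its frequency is unknown. Each subject whose outcome actually turns on the choice of row counts for 2.5 points in a cohort of 40 or 7.1 points in a stage of 14. A subject re-challenged under the Grade 3 exception might not change the discontinuation count at all. The primary endpoints, objective response and pathologic response, are not directly affected. The conclusion rests on one inference, that the Grade 2 row foresees later cycles after a recurrence, and on the readable text alone.

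**What to change.** Reconcile the Grade 2 and Grade 3 rows of Table 6 so that a reaction that resolves and recurs on restart falls under one row only, with a single instruction for acute management, for later study treatment and for any conditions on continuing. Which instruction that should be is for the sponsor's clinicians to decide; no view is taken here. At the same time, check that the grade wording in Table 6 is consistent with the CTCAE v5.0 grading that Section 9.2.2 requires, so that sites do not work from two definitions.

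The cost is a wording change at the next amendment and a note to sites. It needs no additional subjects, visits or data.

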5.4 Treatment Compliance

Study treatment will be administered only by qualified and trained study personnel at the study site. The infusion date and start and stop times will be recorded in the source documents and electronic case report form (eCRF).

5.5 Product Complaints

A product complaint is any perceived deficiency related to physical, chemical, biological properties, or the labeling or packaging of a product.

If the solution is cloudy, is discolored, or contains visible particulate matter, the product must be quarantined under the specified storage conditions, and the deficiency must be reported on a Product Complaint Form as described in the Pharmacy Manual. A Complaint Investigator will follow-up to obtain additional information and provide instructions on how to return the product.

Return of the product must be recorded on the Drug Accountability Log to ensure complete tracking of drug supply.

5.6 Prior and Concomitant Medications and/or Procedures

Medications taken within 30 days prior to the administration of study treatment and all concomitant medications and therapies administered up to the EOT Visit will be recorded in the relevant eCRF. After EOT, only concomitant medications administered for treatment of reported irAEs, AEs \geq Grade 3, and SAEs will be recorded. All anticancer treatments will be reported until the end of the study.

1. Inhaled or intranasal corticosteroids (with minimal systemic absorption) may be continued if the subject is on a stable dose. Nonabsorbed intra-articular steroid injections will be permitted. Systemic corticosteroids required for the control of IRRs or irAEs must be tapered and be at nonimmunosuppressive doses (<10 mg per day of prednisone or equivalent prior to the next study treatment administration). The use of steroids as prophylactic treatment for subjects with contrast allergies to diagnostic imaging contrast dyes will be permitted.
2. The use of herbal remedies for the purpose of treating the subject's cancer (eg, herbal preparation in Chinese traditional medicine), other marketed anticancer chemo/immunotherapy/hormonal drugs, or investigational drugs is not permitted.
3. Vitamins and nutritional supplements are not prohibited.
4. New chemotherapy, hormonal, radiation, or immunotherapy are not permitted during the screening or treatment periods.
5. Palliative/therapeutic therapies (eg, focal radiotherapy for pain, thoracentesis or paracentesis for comfort) are permitted after consultation with the Medical Monitor.

6. Co-administration of bisphosphonates and denosumab is permitted for subjects being administered bisphosphonates and denosumab prior to the study and confirmed to be on a stable dose. These drugs should be continued at the same dose during the study.
7. The use of live vaccines while on study treatment is prohibited. The use of any killed or attenuated vaccines for the prevention of influenza is permitted. The use of other killed or attenuated vaccines for the prevention of infectious diseases may be permitted on a case by case basis after discussion with the Medical Monitor. Any vaccinations administered during the Treatment Period must be documented on the subject's records and in the eCRF.

Any new anticancer therapies (eg, chemotherapy, biochemotherapy, radiation, immunotherapy, or any investigational treatment) for the treatment of the subject's cancer should be recorded in the eCRFs. Note that new anticancer therapies may only be administered after the last dose of study treatment.

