1 INTRODUCTION AND BACKGROUND INFORMATION

This study is composed of 2 distinct documents:

- [REDACTED]
- This CX-072-specific Module (CTMX-M-072-002)

Briefly, [REDACTED], or [REDACTED] is a stable document that contains all study design features typically included in a standard Phase 1-2 clinical study protocol, but without reference to a specific investigational medicinal product (IMP). The Core, which provides the basis for all first in human clinical studies with ProbodTM therapeutics, describes general study procedures such as guidelines for drug accountability, efficacy and safety parameters, and study administrative procedures. The CX-072 Module for this Phase 2 study (this document) is customized for the assessment of the CX-072 ProbodTM therapeutic in combination with ipilimumab at the designated combination doses and provides all guidelines necessary to safely manage subject care. Familiarity with both documents is required for proper conduct of this study.

This core plus module system will enable a comprehensive clinical evaluation of ProbodTM therapeutics within a unified clinical development program that has common components of study design, execution, and assessments, and common Investigator oversight. Where there are overlapping directives between the 2 documents, Investigators are instructed to follow the CX-072 Module regarding subject care guidelines. [REDACTED] for a more detailed discussion of the Core study design and rationale.

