3.7 Estimated Treatment Duration and Study Periods

In Part A, a subject's treatment may continue until confirmed disease progression (assessed by irRECIST), clinical deterioration as defined by the Investigator, withdrawal of consent, other study treatment withdrawal criteria are met, or until the study is terminated, whichever occurs first. In Part B, a subject's treatment duration will continue until progression as defined by RECIST prior to surgery, disease relapse after surgery, clinical deterioration as defined by the Investigator, withdrawal of consent, other study treatment withdrawal criteria are met, the subject has received CX-072 for 1 year postsurgery, or until the study is terminated, whichever occurs first. In Part B, a subject's treatment duration will be up to approximately 15 months (including 1 year postsurgery).

This Module is comprised of 3 periods:

- The Screening Period begins within 30 days prior to the first dose of study treatment (ie, Cycle 1 Day 1 Visit). Subjects for whom consent is provided will undergo Screening Period assessments to determine eligibility for the study; assessments must be performed within 30 days prior to the first dose of study treatment unless otherwise stated in this Module. Subject evaluations and tests performed specifically to determine eligibility (ie, not performed as routine standard of care) may be performed only after the informed consent form (ICF) has been signed. Assessment(s) done per standard of care prior to signing the ICF may be used for eligibility determination if completed within 30 days prior to the first dose of study treatment. The study assessments to be followed are outlined in the Schedule of Assessments in [Table 1](#) (Part A) and [Table 2](#) (Part B).
- The Treatment Period begins with the first dose of study treatment (ie, Cycle 1 Day 1) and continues up to 30 days after the last dose of study treatment (ie, End of Treatment [EOT] Visit). All scheduling is relative to first dose of study treatment (ie, Cycle 1 Day 1).

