9. Unresolved acute toxicity Common Terminology Criteria for Adverse Events (CTCAE) v5.0 \geq Grade 1 (or baseline, whichever is greater) from prior anticancer therapy. Alopecia and other nonacute toxicities are acceptable. Hormone deficiency due to prior anticancer therapy, that is deemed stable with supplementation or does not require supplementation is allowed.
10. History of severe allergic or anaphylactic reactions to human mAb therapy or known hypersensitivity to any Probody therapeutic
11. Subjects with known human immunodeficiency virus, acquired immune deficiency syndrome, or any related illness
12. Subjects with acute or chronic hepatitis B or C
13. History of allogeneic tissue/solid organ transplant, stem cell transplant, or bone marrow transplant
14. Major surgery (eg, that required general anesthesia) within 4 weeks prior to the first dose of study treatment (and must be confirmed to be completely healed), or minor surgery (eg, not involving chest, abdomen, or intracranial structures) or gamma knife treatment (with adequate healing) within 14 days prior to first dose of study treatment (excluding biopsies conducted with local/topical anesthesia) if complete healing is confirmed
15. History of active malignancy not related to the cancer being treated within the previous 2 years, with the exception of localized cancers that are considered cured and, in the opinion of the Investigator, present a low risk for recurrence. These exceptions include, but are not limited to, basal or squamous cell skin cancer, superficial bladder cancer, and carcinoma in situ of the prostate, cervix, or breast.
16. Received a live vaccine within 30 days prior to the first dose of study treatment. Examples of live vaccines include, but are not limited to, the following: measles, mumps, rubella, chicken pox/zoster, yellow fever, rabies, Bacillus Calmette-Guérin, and typhoid vaccine.

17. Intercurrent illness including, but not limited to:

- Ongoing severe aortic stenosis
- Myocardial infarction or stroke within 24 weeks prior to first dose of study treatment
- Any of the following within 12 weeks prior to first dose of study treatment: symptomatic congestive heart failure (ie, New York Heart Association Class III or IV), unstable angina pectoris, or clinically significant and uncontrolled cardiac arrhythmia
- Nonhealing wound or ulcer within 4 weeks prior to Cycle 1 Day 1

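### Section 5.6, item 7 bans live vaccines on study treatment, then permits attenuated influenza vaccine with no Medical Monitor step

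*Combined protocol and SAP*

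**What the plan says.** Section 5.6 (Prior and Concomitant Medications and/or Procedures), item 7, has four sentences.

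1. A ban: "The use of live vaccines while on study treatment is prohibited".
2. A permission for influenza: "The use of any killed or attenuated vaccines for the prevention of influenza is permitted".
3. A conditional permission for everything else: "The use of other killed or attenuated vaccines for the prevention of infectious diseases may be permitted on a case by case basis", subject to discussion with the Medical Monitor.
4. A recording rule: "Any vaccinations administered during the Treatment Period must be documented on the" subject's records and in the eCRF.

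Section 4.6, exclusion criterion 16, applies to the period before dosing. It excludes anyone who "Received a live vaccine within 30 days prior to the first dose of study treatment". It lists examples of live vaccines, says the list is not exhaustive, and names no influenza vaccine.

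**The concern.** Sentences 1 and 2 of item 7 give opposite answers for one product class, live attenuated influenza vaccine. A site that relies on the influenza sentence could give such a vaccine during study treatment without asking anyone, although the sentence before it forbids this.

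Subject safety and site compliance are at stake; the statistics are not. The plan itself treats live vaccines as a hazard in this population, since it bars them both before and during treatment. It also expects some subjects to be immunosuppressed: Section 5.3.3 directs corticosteroids for immune-related toxicity and lists agents such as infliximab and mycophenolate as further options. Section 5.3.3.1 allows treatment to resume on low-dose corticosteroid after colitis.

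**Working it through.** The plan states no figure on this point and no formula applies. The check is a comparison of the text.

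**Step 1: what the key word means.** The supplied text does not define *attenuated*. In ordinary usage it describes a weakened live organism, and the non-live partner of *killed* is *inactivated*. If *attenuated* were meant as non-live, pairing it with *killed* would add nothing.

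**Step 2: apply each sentence to each kind of vaccine.**

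| Vaccine given on study treatment | Sentence 1 | Sentence 2 | Sentence 3 | Result |
|---|---|---|---|---|
| Killed influenza | Not caught | Permitted, no condition | Not applicable | Consistent |
| Live attenuated influenza | Prohibited | Permitted, no condition | Not applicable | Contradiction, no outside check |
| Other killed | Not caught | Not applicable | Possible after Medical Monitor discussion | Consistent |
| Other live attenuated | Prohibited | Not applicable | Possible after Medical Monitor discussion | Contradiction, but with a check |

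**Step 3: look for something that settles it.**

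- Item 7 contains no order of precedence among its sentences.
- Sentence 4 requires a vaccination to be recorded. It does not prevent one.
- Exclusion criterion 16 shows the same intent as sentence 1, but it covers only the 30 days before the first dose. A site that consults its examples finds no mention of influenza.

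**Step 4: extent in the text.** Item 7 has 1 ban + 2 permissions + 1 recording rule = 4 sentences. Both permissions (2 of 2) use the faulty wording. One of the two, the influenza sentence, lacks a Medical Monitor step, so the unguarded case is influenza alone.

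**Step 5: test the replacement.** With *inactivated (non-live)* in sentences 2 and 3, the two contradictory rows are governed by sentence 1 only and the two consistent rows do not change. The item then agrees with itself and with criterion 16.

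**The case against.** The strongest reply concerns weight. The ban stands immediately before the permission in the same numbered item, so a reader taking the item in order can treat the permissions as operating inside the ban. Both provisions that name live vaccines point the same way. The influenza sentence permits but does not oblige, so a site that follows the ban breaks nothing. The documents do not show that any site has misread the item, that live influenza vaccine is in use at the sites, or what risk it would carry here. The meaning of *attenuated* comes from general vocabulary and not from the protocol.

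Most of this stands, and it is why the point is rated minor. It does not remove the contradiction. An instruction used at approximately 40 sites (Section 3.2) should not need the reader to infer that one sentence silently limits the next, least of all where the permission covers *any* such vaccine and nobody has to be consulted.

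Two supporting arguments are open to challenge, and the conclusion rests on neither. Section 1 gives the Module priority over the Core where their directives overlap, but the Core is not in the supplied text, so whether it covers vaccines cannot be checked. Section 3.7 allows Part B treatment of up to about 15 months, which makes an influenza vaccination during treatment foreseeable, but that is a maximum and says nothing about use of live vaccine.

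A last objection is that *killed or inactivated* might seem to leave out non-live vaccines made without whole organisms. The present wording does not name those either, so the replacement narrows nothing, and the bracketed *non-live* makes the intent plain.

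**Conclusion.** The concern holds. Item 7 both prohibits and permits live attenuated influenza vaccine during study treatment, and nothing else in the supplied documents resolves the conflict. The intended rule is almost certainly prohibition.

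The finding is small: a wording error in two sentences, one of them without a safeguard. No number of affected subjects can be derived, and none is claimed. Sample size, error rates and the primary analysis are unaffected. The conclusion rests on one assumption, that *attenuated* carries its usual meaning of weakened but live. Because this is a working safety instruction and the remedy costs almost nothing, it should be corrected.

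**What to change.** In sentences 2 and 3 of Section 5.6, item 7, describe the permitted vaccines as *killed or inactivated (non-live)*. Plain *non-live* would serve equally well.

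Preferably also extend sentence 1 so that the ban expressly includes live attenuated influenza vaccine. Adding that product to the examples in exclusion criterion 16 is optional, because the criterion already bars any live vaccine.

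The cost is two word replacements and one optional phrase. Non-live influenza vaccine stays available to all subjects without consultation, and no procedure, data collection or analysis changes. A stand-alone amendment is not needed: opening Stage 2 of Cohort A2 already requires one (Sections 1.5.3 and 3.3), and the edit can go in then or in any earlier amendment.
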